2.3 RISK/BENEFIT ASSESSMENT

2.3.1 KNOWN POTENTIAL RISKS AND THEIR MITIGATION

Quality and risk management plan

To mitigate risks, an Integrated Quality & Risk Management Plan has been developed. The plan provides a summary of highest-scoring risks: delay in investigational products availability; failure to meet enrollment target; and high rate of missed assessments. In addition, the Risk Matrix provides details on risks to quality, along with mitigation strategies and risk scores.

Risks from metformin

Metformin is contraindicated in persons with an estimated glomerular filtration rate (eGFR) of less than 30 mL/min. For persons with an eGFR of 30 to 45 mL/min, metformin can be continued with caution but a reduction of the dose or discontinuation of the medication can be considered; in this range, it is also recommended that persons do not initiate metformin. Thus, participants with eGFR < 45 mL/min will not be eligible to participate. The risk of lactic acidosis is increased in persons with liver disease and class III or IV congestive heart failure. Thus, persons with liver disease other than non-alcoholic-fatty liver disease or class III or IV congestive heart failure will not be eligible to participate due to the risks of side effects. Non-alcoholic fatty liver disease is allowed given that it may benefit from metformin, unless it is at the cirrhosis stage.

Participants will be cautioned that IP be discontinued the day before any surgery or administration of contrast agents and may be resumed 48 hours after the procedure. We will monitor these contingencies on a monthly basis, and ad-lib as needed by the participant. We will also tell participants to avoid excessive intake or binge intake of alcoholic beverages. The Centers for Disease Control (CDC) define excessive alcohol intake as 15 drinks or more a week in men, and 8 drinks or more in women. The CDC defines binge

drinking as 5 or more drinks consumed on one occasion for men, and 4 or more drinks consumed in one occasion for women. The United States standard drink sizes are 12 ounces of 5% alcohol by volume (ABV) beer, 8 ounces of 7% ABV malt liquor, 5 ounces of 12% ABV wine, and 1.5 ounces of 40% ABV (80-proof) distilled spirits or liquor (e.g., gin, rum, vodka, whiskey).

Hypoglycemia should not occur because participants are not diabetic and should not be on other diabetes medications. If participants develop diabetes by HbA1c criteria (6.5% or higher) they will be referred to their physicians to decide about treatment for diabetes. This may lead to discontinuation of IP upon consultation with the study's safety officer at the DCC. However, participants will be invited to remain in the study and will be analyzed following intent to treat. We will call these participants every month to follow-up.

As mitigation, B12 levels, complete blood count, hepatic function, and kidney function will be tested every six months. Development of suspected side effects or contraindications to metformin will lead to stoppage of the medication upon consultation with the medical monitor.

We will call participants every month to ask about side effects such as the following:

- Very common (>1/10)
 - Gastrointestinal disorders such as nausea, vomiting, diarrhea, abdominal pain, and loss of appetite.
These undesirable effects occur most frequently during initiation of therapy and resolve spontaneously in most cases. A slow increase of the dose may also improve gastrointestinal tolerability. Gastrointestinal disorders are the most common reason for metformin non-tolerance.
- Common side effects (>1/100):
 - Taste disturbance.
- Very rare side effects (<1/10,000):
 - The most severe but very rare side effect of metformin is lactic acidosis.
 - Metformin has also been reported to cause vitamin B12 (cobalamin) malabsorption and decrease in serum levels that can lead to megaloblastic anemia.
 - Liver function abnormalities
 - Skin reactions such as erythema or pruritus
 - Tachycardia

Adequacy of protection against risks

a. Informed Consent

Potential participants may contact the study coordinator/research assistant, or the latter may contact potential participants using available contact information. The usual contact will be via telephone, but could include email, or mail. At first contact by telephone the study will be briefly explained and the interest to participate will be explored. If the individual wants to participate, he/she will be screened for inclusion and exclusion criteria. If the individual is eligible, an appointment for a screening visit will be made. At that time, the consent form will be reviewed and if appropriate, signed by the participant and coordinator. A copy of the consent form will be provided to the participant for his or her records. The consent form will specifically request consent for the future use of data and stored serum and plasma for ancillary studies.

b. Protections Against Risk

Privacy/confidentiality. The EDC will automatically assign each participant with an ID number that will be used for all study documents.

Risks from neuropsychological testing

Participants will be clearly told as part of the written consent and verbally that they can opt out of the study at any time if they do not wish to carry out the testing. We will reschedule the testing as desired by participants if they wish to continue.

Risks from interviews

The interviews and cognitive testing may cause psychological distress in participants. Our staff in charge of data collection will be bilingual as needed, trained in cultural competence and have at least 3 years of experience in the administration of cognitive batteries. We have never had to respond to a contingency or complaint related to the administration of interviews or cognitive testing.

Risks from physical assessments

The measurement of vital signs and anthropometrics may cause psychological distress and physical discomfort.

Risks from phlebotomy

The total amount of blood drawn for clinical diagnostic evaluation will not exceed 60 mL. Venipuncture could result in transient discomfort, pain, bleeding, an ecchymosis (a.k.a. bruising), and in the worst-case scenario, a hematoma. Significant bleeding is highly unlikely in the absence of a bleeding or coagulation disorder. The study personnel will be instructed to maintain pressure with gauze on the venipuncture site for at least 10 minutes. In the case of persistent bleeding, the investigators will be called immediately. A hematoma is highly unlikely, but in a worst-case scenario could result in a compartment syndrome.

If participants report any discomfort or complication from phlebotomy or other physical assessment (e.g., hematoma), site PIs or study physicians will be called immediately to assess the problem and decide on further actions including referral to the emergency room.

Risks from brain imaging procedures

We will exclude from the study any participant who reports contraindications to MRI. If a participant becomes anxious and cannot complete any imaging procedures, or if a contraindication is found at the time of the imaging procedures, they will be excluded from undergoing brain MRI. Brain MRI may show abnormalities during a safety read conducted by a site radiologist within 24 hours of the scan. These findings are communicated to site investigators who take the appropriate action. Incidental MRI findings are classified in four levels following a standard protocol:

- Level 1: No medically significant findings. No referral necessary.
- Level 2: Minor findings without medical significance (e.g., white matter hyperintensities). No referral necessary.
- Level 3: Expedited, but non-urgent medical evaluation recommended within 2 weeks (e.g., apparent meningioma without signs of mass effect).
- Level 4: Acute abnormal findings requiring immediate medical attention (e.g., acute stroke or space occupying lesion with mass effect).

The estimated total radiation a participant will receive from the maximum of 2 PET scans repeated after approximately 18 months is 24.88 mSv (including the radiation of the 2 injections of florbetaben and MK-6240 and the radiation from the 2 CT scans, repeated after 18 months), similar to the radiation that the average person in the United States is exposed to in 48 months (4 years).

Potential risks from MRI. All participants willing to undergo MRI will be questioned for exclusion criteria, including claustrophobia and the presence of foreign bodies not acceptable for MRI. While there have been no reports of any harmful long-term effects caused by a 3.0 T magnet, or magnets of even higher

strength, the long-term effects of being placed in a magnet of this strength are not known. Some people may experience nervousness or discomfort due to the scanner's small space and the need to lie still during the scans. Other than for pacemakers, some types of metallic implants and medication patches (which are contraindications to MRI participation), we are not aware of any other potentially dangerous interactions with the MRI scan. Since the MRI scanner produces loud "knocking" noises; participants will be provided with earplugs for their comfort. If any discomfort is experienced and participants wish to stop the scan, they can inform the MRI technologist and the scan will be stopped immediately. In our experience, no one has had ongoing sensations from the MRI scan once the scanning has stopped.

Potential risks from PET scans. The risks from PET scans include risks from phlebotomy, similar to those described above, and from exposure to radiation. The procedures involving radiation in this research study will expose each participant to a very small amount of radiation (24.88 mSv total for the maximum of two florbetaben scans and two MK-6240 scans over approximately two years), in addition to the amount that they might receive from normal medical care. There may be an increase in the chances of developing cancer many years after this study. The additional risk from this research study is less than 0.15% (1 in 705). At this very low level, scientists are uncertain as to the actual risk from research and there may be no risk at all.

Risks to confidentiality

Health Insurance Portability and Accountability Act (HIPAA), and data safety and security: only the PI and approved study personnel will have access to individually identifiable private information.

ID assignment. In compliance with HIPAA, individual participant confidentiality is assured through the use of ID codes. These ID numbers will be automatically assigned by the EDC (managed by the DCC) and will not contain protected health information (PHI) (e.g., social security number, medical records number, etc.). Case report forms will be identified only by ID numbers. Data processing and analyses will not permit identification of any individual. Linkage between individual and ID number will only be accessible by site personnel and the monitoring personnel.

Data transfer. It is assumed that all PHI will be collected after informed consent; as a result, certain PHI (e.g., date of birth) that are necessary for analyses may be entered as part of the data set.

Monitoring risks

Routine monitoring of study data will take place to ensure timely entry of study data, data quality and data integrity. The monitoring team will compile and track the following quality metrics:

- **Major protocol violations** – number of major protocol violations per participant at a site and the total count of violation divided by the number of participants in the study.
- **Major audit findings** – number of major audit findings per site and across the sites in the study.
- **Time to query resolution** – the average number of days between query issuance and resolution on a per-site and overall study basis.
- **Visit entry time** – the average time within a site for entry of visit data, calculated as elapsed days between the Date of Screening/Date of Visit and the first date that the status of that page was set to IN REVIEW.
- **Actual vs. planned spending** – the ratio of actual costs (both quarterly and annual) as a percentage of the planned budget for that year.
- **Enrollment rate** – the rate of enrollment by site and for the entire study, annualized and normalized by the duration of a site's participation to allow cross-site comparisons. Specifically, RND/Site-Year is calculated as #RND*365/#days elapsed since site activation.

- **Missingness rate** – the number of missed data points divided by the number of expected data points given the participants' status and progress. The denominator is difficult to calculate in an automated manner; a visual estimate on a sampling of participants is sufficient for the purposes of assessing site data quality.
- **Query rate** – the number of queries for a site divided by the number of case report form (CRF) pages accrued by the participants at that site as of a specific point-in-time.

Addressing medical and mental health contingencies. It is possible that during a study visit the staff or investigators encounter a medical contingency. The Table of Medical Contingencies (below) describes the protocol for such contingencies.

CONDITION	ACTION
Blood pressure problems as reported by participant	
High or low blood pressure	Refer to emergency room/call 911, or walk-in PMD's office immediately
Diabetes	
If dizzy and/or hypoglycemic by fingerstick	Administer juice, other sweet beverage, or food by mouth; if improved within 15 minutes, advise to consult with PMD the same day; if not better, refer to emergency room/call 911
Complaining of polydipsia polyuria, FS >200 mg/dl	Refer to emergency room/call 911
FS >200 mg/dl and asymptomatic	If treatment has not been taken, advise to take it If treatment has been taken, advise consultation with PMD the same day
Falls	
Fall during motor assessment or any other circumstance	Call PI or study physician; take to emergency room.
Respiratory	
Chest pain	If cardiac etiology cannot be ruled out clinically, refer to emergency room/call 911 If accompanied by diaphoresis or respiratory distress, refer to emergency room/call 911 If chest pain clearly not cardiac, consultation with PMD the same day
Asthma/COPD exacerbation	If improved with treatment available at home, consultation with PMD the same day. Otherwise, refer to emergency room/call 911
Other respiratory distress	Refer to the emergency room/call 911
Psychiatric/social	
Depression/anxiety	If no potential harm to self or others, consult with PMD or mental health provider the same day Take prescribed medications not already taken If potential harm to self or others, refer to the emergency room/call 911
Any condition with acute changes in mental status	Refer to the emergency room/call 911
Neglect	If potential harm to self-apparent within 24 hours, refer to emergency room/call 911 If medical condition suspected as cause, refer to emergency room/call 911

CONDITION	ACTION
	In other situations, notify social worker and next of kin
Other	
Leg edema	If acute, refer to emergency room/call 911 or walk-in clinic If sub-acute, consult with PMD the same day
Failure to thrive	Refer to emergency room/call 911
Apparent dehydration	Refer to emergency room/call 911
Fever	Consultation with PMD the same day
Vomiting/diarrhea	If unable to hydrate by mouth, refer to emergency room/call 911; otherwise, advise consultation with PMD the same day. Withhold study medication until vomiting and diarrhea have stopped, and dehydration has resolved.
Headache	If clearly migraine or tensional headache, advise to take prescribed medications; if no improvement, consult with PMD same day. If no changes in mental status or neurologic deficits, if blood pressure <160, consultation with PMD same day; otherwise, refer to emergency room/call 911
Weight loss/no medical follow-up	Consult with PMD the same day If no PMD, see contacts below
Acute renal insufficiency (azotemia), for any reason, including post-renal (e.g., obstruction), pre-renal (e.g., dehydration), or intrinsic (e.g., acute tubular necrosis)	Stop IP until the cause of acute renal insufficiency has resolved and renal function has improved to at least a GFR of 45 mL/min or higher
Any other condition treated	Advise consultation with MD. Provide contact numbers (see below)
IF IN DOUBT	Contact PI or study physician

Table 6. Medical Contingencies: Summary of Conditions and Actions

Vulnerable participants

No vulnerable populations will be included in this study.

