1.3 STUDY DURATION

Recruitment is planned to end such that data collection in the phase II study in 326 participants can be completed by approximately April 30, 2026. Analyses and decision to proceed to a phase III trial would occur within 6 months of end of the phase II study. The Figure above shows the proposed schedule of assessments per participant. After telephone screening and preliminary determination of eligibility, participants will have an in-person screening visit. If they meet criteria for amnestic mild cognitive impairment (aMCI), the baseline visit will be completed. If blood tests do not show exclusion criteria, participants will be randomized, followed by a drug titration period. Metformin/placebo, referred to as Investigational Product (IP) from here on, will be titrated every 10 days by one tablet (500 mg), up to 2000 mg a day. The neuropsychological battery, clinical interviews, physical exam, study partner interview, and phlebotomy, will be conducted at baseline and repeated every 6 months for 18 months, for a total of four visits. Brain imaging including brain MRI and amyloid and tau PET will be conducted in up to 186 participants (186). Baseline brain imaging will be conducted after the baseline visit and after the 18 months assessment. Medication compliance and adverse events will be checked every month via telephone call, text, or email, and in person during the scheduled in-person assessments every six months.

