- Vision and hearing must be sufficient for compliance with testing procedures.
- Must have a study partner to come to all appointments or be available by telephone at follow-up visits.

Study Partner Inclusion Criteria

- The study partner can provide an independent evaluation of functioning for a person enrolled in the MAP study as a participant.
- The study partner agrees to attend study visits with the MAP participant or be available by telephone.

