6.4 STUDY INTERVENTION COMPLIANCE

Compliance with the study intervention will be monitored by direct discussion at monthly telephone calls and face-to-face study visits (every six months).

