- During follow-up, if the participant develops dementia, indicated by a clinical dementia rating summary score of 1 as determined in the previous follow-up assessment. If the participant demonstrates capacity, he/she may consent; if the participant lacks capacity but wants to continue participation, a legally authorized representative will need to provide consent after the participant's assent. It is important to point out that this approach respects the participant's decision at baseline to participate in the study, when he/she had the capacity to consent.

Participants will be given three trials to respond to the UBACC. If after three trials they do not have a perfect score, they will be determined to lack capacity to consent. The determination of lacking capacity to consent will lead to exclusion at baseline, and to the need for a legally authorized representative to provide consent during follow-up. We expect that the contingencies described above will occur in less than 5% of the participants in the study, who will have mild cognitive impairment at baseline.

Medical history, medications

Detailed medical, surgical, and psychological history, and all medications utilized, including a judgment as to whether they affect cognition (positively or negatively) will be collected at baseline. Psychiatric history, current and past history of depression, current anxiety, alcohol and other substance use, head injury, hypertension, cardiac disease, thyroid disease, other major medical conditions, and surgery are evaluated at the baseline visit. A full medical history will be obtained only at the baseline visit. Any report of events, or side effects will prompt a full history and physical exam at follow-up visit. A COVID-19 questionnaire will be administered at every visit.

Physical Assessments (vital signs, anthropometric measures, brief neurologic exam)

A brief neurologic exam will be conducted at the in-person screening visit. Participants must also be assessed for signs of congestive heart failure, pulmonary, liver or renal disease as contraindications to

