8.3 ADVERSE EVENTS AND SERIOUS ADVERSE EVENTS

8.3.1 DEFINITION OF ADVERSE EVENTS (AE)

Adverse events

Adverse event (AE) means any untoward medical occurrence associated with the use of an intervention in humans, whether or not considered intervention related. An AE can therefore be any undesirable sign,

symptom or medical condition occurring after starting IP, even if the event is not considered to be related to the pharmaceutical product. An AE can arise with any use of the drug (e.g., off-label use, use in combination with another drug) and with any route of administration, formulation, or dose, including an overdose (21 CFR 312.32 (a)). Headache, dizziness, lightheadedness, and gastrointestinal upset are AEs that will be specifically questioned about during phone calls and study visits.

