8.3.4 TIME PERIOD AND FREQUENCY FOR EVENT ASSESSMENT AND FOLLOW-UP

Participants will have assessments including phlebotomy for safety laboratory every 6 months including baseline, 6-months, 12-months, and 18-months visits. In addition, participants will have monthly calls for monitoring of adverse events between visits. The safety laboratory tests will include complete blood count, basic metabolic panel, hepatic panel, and vitamin B12 (cobalamin). Cobalamin testing will allow to assess whether participants develop cobalamin deficiency and anemia, which could be due to metformin, or contraindications to metformin use such as hepatic insufficiency and severe renal insufficiency.

At each study visit, the investigator will inquire about the occurrence of AE and SAEs since the last visit. All AEs and SAEs will be captured on the appropriate eCRF. All AEs and SAEs occurring while on study drug

will be documented appropriately regardless of relationship. All AEs and SAEs will be followed to adequate resolution.

Any medical condition that is present at the time that the participant is screened will be considered as baseline and not reported as an AE. However, if the study participant's condition deteriorates at any time during the study, it will be recorded on the appropriate eCRF (e.g., AE or SAE).

Changes in the severity of an AE or SAE will be documented to allow an assessment of the duration of the event at each level of severity to be performed. AEs and SAEs characterized as intermittent require documentation of onset and duration of each episode.

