10.1.1.2 Consent Procedures and Documentation

Informed consent will be conducted in person, electronically, or remotely by video or telephone using a hard-copy (paper) ICF.

Informed consent is a process that is initiated prior to the individual's agreeing to participate in the study and continues throughout the individual's study participation. Consent forms will be IRB-approved and the participant will be asked to read and review the document. The consent designee will explain the research study to the participant and answer any questions that may arise. A verbal explanation will be provided in terms suited to the participant's comprehension of the purposes, procedures, and potential risks of the study and of their rights as research participants. Participants will have the opportunity to carefully review the written consent form and ask questions prior to signing. The participants should have the opportunity to discuss the study with their family or surrogates or think about it prior to agreeing to participate. Participants must be informed that participation is voluntary and that they may withdraw from the study at any time, without prejudice. A copy of the signed ICF will be given to the participants for their records. The informed consent process must be conducted, and the form signed, before the participant undergoes any study-specific procedures. The rights and welfare of the participants will be protected by emphasizing to them that the quality of their medical care will not be adversely affected if they decline to participate in this study.

MAP requires the participation of a study partner who should be available by telephone or in person to answer questionnaires about the participant's cognition, mental health, and function. The study partner must provide verbal consent to participation. The consent designee will read a consent script and document that the study partner verbally consented to participation in the MAP trial. The waiver of written documentation of consent is available only to study partners, not to study participants.

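### Monthly safety questions are directed to memory-impaired participants and the study partner is given no safety question, so some adverse events and reasons to hold drug may be missed or reported late between visits.

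*Protocol*

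**What the plan says.** **Who is asked.** Under the metformin risks, section 2.3.1 says: "We will call participants every month to ask about side effects such as the following". Section 8.3.4 says "participants will have monthly calls for monitoring of adverse events between visits". Section 1.3 adds the mode: "Medication compliance and adverse events will be checked every month via telephone call, text, or email". Section 6.4 says "Compliance with the study intervention will be monitored by direct discussion at monthly telephone calls and face-to-face study visits". For surgery and contrast agents, section 2.3.1 has participants cautioned about interrupting study drug. It checks for these situations monthly, and otherwise when the participant needs it.

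**Who the participants are.** Section 5.1 requires abnormal delayed paragraph recall for both early and late MCI. For follow-up, section 8.1 says that "if the participant lacks capacity but wants to continue participation, a legally authorized representative will need to provide consent", given after the participant's assent.

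**What the partner does.** Section 5.1 sets as a criterion: "The study partner agrees to attend study visits with the MAP participant or be available by telephone". Section 10.1.1.2 says "MAP requires the participation of a study partner who should be available by telephone or in person to answer questionnaires", and gives their subjects as cognition, mental health and function. The partner consents verbally. The assessment rows in the partner block of Table 7 are consent, CDR, ADCS-ADL-PI and MBI. The rows for monthly calls, dose log and adverse events stand outside that block.

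**Which symptoms are asked about.** Section 8.3.1 says: "Headache, dizziness, lightheadedness, and gastrointestinal upset are AEs that will be specifically questioned about during phone calls and study visits". Sections 2.3.1 and 8.2 each give a different set.

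**The concern.** The monthly contact is where the trial learns promptly of side effects and of events that bear on interrupting study drug. Sections 2.3.1, 5.3 and 8.3.8 name such events: surgery, contrast procedures, vomiting or diarrhoea, acute renal failure, hospitalisation for infection, and new contraindications. The informant named for that contact is a person selected for poor delayed recall, and the contact may be no more than a text or an email.

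The trial already takes separate participant and partner reports on the CDR and the ADCS-ADL-PI. It therefore has a second informant on function but not on safety. After loss of capacity the protocol changes who consents, but says nothing about who answers the safety questions.

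At stake are the completeness of the adverse-event record in both arms and the timeliness of drug interruptions that depend on someone reporting an event.

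**Working it through.** This is a comparison of passages. No figure in the plan needs reproducing, and arithmetic serves only for scale.

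1. *Monthly informant.* Sections 2.3.1 and 8.3.4 name participants. The titration and monthly-call items in section 8.1, and the adverse-event and dose-log rows of Table 7, name no informant. No passage puts an adverse-event, hospitalisation, procedure, contraindication or compliance question to the partner or to a legally authorised representative.

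2. *Share of contacts that depend on this route.* Monthly contacts run from month 1 to month 18. Three of those months (6, 12 and 18) are visits, so 18 − 3 = 15 contacts fall between visits.

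3. *Safeguards at visits.* Section 8.3.4 has the investigator ask at each visit about adverse events since the last one. Section 8.3.8 has the investigator ask about hospitalisations, surgery and procedures affecting dosing. Section 2.3.1 schedules blood count, hepatic, renal and B12 tests every six months, which do not depend on recall. These limit what is lost for good. They cannot supply timely notice of a procedure or an acute illness between visits. The visit enquiries also name no informant.

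4. *Size of the group that loses capacity.* Section 8.1 expects the situations calling for a capacity assessment in fewer than 5% of participants: 0.05 × 326 = 16.3, so at most about 16. Those who then continue, and those still on study drug, are subsets for which the protocol gives no number.

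5. *Partner access.* Note c to Table 7 has the CDR completed with the partner at screening/baseline and at months 6, 12 and 18. Three follow-up partner interviews thus already exist. No monthly partner contact does.

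6. *Solicited symptoms, side by side.*
   - Section 2.3.1: gastrointestinal symptoms including appetite loss, taste disturbance, lactic acidosis, B12 malabsorption, liver abnormalities, skin reactions and tachycardia.
   - Section 8.2: gastrointestinal symptoms and development of contraindications.
   - Section 8.3.1: headache, dizziness, lightheadedness and gastrointestinal upset.

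   Only gastrointestinal symptoms are common to all three.

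**The case against.** **The protocol does not forbid asking the partner.** This stands. A reader might infer that participants are the only permitted source, but that is inferred from silence. The synopsis says in general terms that the partner answers questions about the participant, and section 10.1.1.2 describes the partner's questionnaires without excluding others. What the documents support is that the partner is given no safety question.

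**Events would be late, not lost, and the participants are only mildly impaired.** This largely stands. Entry requires a CDR of 0.5, an MMSE floor, no dementia and capacity to consent, and nothing in the protocol says such people cannot report a month's symptoms. A reader might infer that events will certainly be missed; the documents support only that some may be missed or reported late.

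**Those who lose capacity need not stay on drug.** This also stands. Section 8.1 allows continued participation but does not mention continued dosing. Section 7.2 lets the investigator withdraw someone who newly meets a relevant exclusion criterion, and section 5.2 lists dementia and lack of capacity among the exclusions. The group is small, but for anyone who does continue the safety informant is still unnamed.

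**A loss of power to detect harm cannot be computed.** A reader might want to attach one. The protocol states no between-arm test of adverse-event rates (section 9.4.4 plans tabulation of serious events) and gives no rate at which events go unreported, so any such figure would rest on assumed inputs.

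**The symptom lists can coexist.** In part. Section 2.3.1 is illustrative, and some of its entries are laboratory findings that nobody can be asked about. But sections 8.2 and 8.3.1 also differ, and a site cannot tell which questions are standard.

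**Conclusion.** The point holds as a weakness in how safety information is gathered between visits. It is not a numerical error or a threat to the primary analysis. The protocol directs monthly safety enquiry to participants enrolled for abnormal recall and assigns the mandatory, consented partner no part in it. Some adverse events and reasons to hold drug may be missed or reported late.

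Its extent cannot be quantified from the protocol. The scale is 15 of 18 monthly contacts, with a particularly exposed group of at most about 16 of 326 if the protocol's own expectation is right. The conclusion assumes that sites follow the text as written and do not routinely question partners on safety. It merits a change because a better informant is already in the trial at little cost.

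**What to change.** - In section 8.1 (follow-up visits), section 8.3.4 and the partner block of Table 7, put the adverse-event, hospitalisation, planned-procedure and new-contraindication questions to the study partner at the six-monthly interviews already scheduled. Extend the partner's role in section 10.1.1.2 to match.
- Record on the adverse-event form who reported each event.
- In section 8.1 (monthly calls) and section 8.3.4, for a participant who remains in the study after a CDR of 1 or higher or loss of capacity, include the partner or the representative in the monthly safety contact.
- Reconcile the symptom lists in sections 2.3.1, 8.2 and 8.3.1 into one standard set of questions, kept apart from findings that only laboratory tests can show.

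None of this alters a dose, a rule for holding drug, an endpoint or the sample size. The cost is a few minutes of partner time per interview, a small number of new monthly partner contacts, a change to the partner consent script and protocol needing sIRB approval, and more minor events to code.
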